2.1 OUTCOME MEASURES

2.1.1 Primary Efficacy Outcome Measure

The primary outcome measure for this study is as follows:

- DFS will be defined as the time from randomization until the date of the first local, regional, or distant melanoma recurrence, occurrence of new primary melanoma, or death from any cause. The DFS component of melanoma recurrence will be assessed by the investigator. The DFS component of an occurrence of a new primary melanoma will be based upon the diagnosis made by a Roche-designated central pathology laboratory. See Protocol Section 4.5.1.4 for histopathologic and imaging requirements for documentation of recurrence.

2.1.2 Secondary Efficacy Outcome Measures

The secondary outcome measures for this study are as follows:

- Distant metastasis-free survival (DMFS) will be defined as the time from randomization until the date of diagnosis of distant (i.e., non-locoregional) metastases or death from any cause.
- Overall survival (OS) will be defined as the time from randomization to the date of death from any cause.

2.1.3 Exploratory Efficacy Outcome Measures

The exploratory outcome measures for this study are as follows:

- Retrospective identification of study patients whose tumors harbor non-E, activating mutations of BRAF kinase at amino acid position 600 (e.g., BRAF^{V600K}), with use of DNA sequencing methods as a means to assess clinical outcomes in this patient subgroup
- Levels of candidate tumor biomarkers in plasma and serum (e.g., circulating mutant *BRAF* DNA) at different timepoints during the study compared with baseline as a means to monitor for and predict melanoma recurrence or occurrence of a new primary melanoma
- Candidate tumor biomarkers at the protein, RNA, and DNA levels (including *RAS* mutations) that may characterize the molecular phenotype of tumors at melanoma recurrence or occurrence of a new primary melanoma as well as predict development of resistance to adjuvant vemurafenib treatment

- Molecular characterization of squamous cell carcinoma (SCC; cutaneous [including keratoacanthoma/KA] and non-cutaneous) or other new primary neoplasms that may be observed in patients treated with vemurafenib

2.1.4 Pharmacokinetic Efficacy Outcome Measures

The pharmacokinetic (PK) outcome measures for this study are as follows:

- Plasma concentrations of vemurafenib at clinically relevant timepoints, including steady-state trough values as well as those associated with diagnosis of SCC, dose interruption, and/or reduction for toxicity, melanoma recurrence, and occurrence of a new primary melanoma

2.1.5 Safety Outcome Measures

The safety outcome measures for this study are as follows:

- Incidence, nature, and severity of adverse events, serious adverse events, and adverse events of special interest. Severity will be graded according to National Cancer Institute Common Terminology Criteria for Adverse Events (NCI CTCAE), v4.0.
- Changes from baseline in ECG findings and targeted clinical laboratory analytes during the course of study treatment

2.1.6 Patient-Reported Outcome Measure

The patient-reported outcome (PRO) measure for this study is as follows:

- To assess patient-reported symptoms, functional interference, and health-related quality of life in the vemurafenib and placebo treatment arms with use of European Organisation for Research and Treatment of Cancer 30-item Quality of Life Questionnaire (EORTC QLQ-C30)

2.2 DETERMINATION OF SAMPLE SIZE

The overall Type I error (α) for this study is 0.05 (two sided). The primary objective of the protocol to assess efficacy as measured by DFS will be evaluated separately for each of the two cohorts. The sample size determination was evaluated separately for each cohort.

2.3 SAMPLE SIZE AND ANALYSIS TIMING

The final primary efficacy endpoint (DFS) analyses for the two cohorts will be conducted according to the procedure specified in Section 4.4.1.

2.3.1 Cohort 1

The final analysis of the primary endpoint of DFS for Cohort 1 will take place when approximately 120 DFS events have occurred, on the basis of the following assumptions:

- Two-sided, stratified log-rank test at the 0.05 significance level

- 80% power
- Median DFS for the control arm of 24 months and estimated median DFS in the vemurafenib treatment arm of 40 months (which corresponds to a hazard ratio [HR] of 0.60)
- 5% annual loss to follow-up for DFS
- No interim analysis

Assuming an accrual rate of 8 patients per month in Cohort 1 and a 17-month ramp-up period to reach steady-state enrollment, approximately 300 patients will be required to be enrolled in Cohort 1 during 43 months and followed for an additional 7 months in order to observe 120 DFS events.

On the basis of the assumptions above, 120 DFS events are projected to occur in Cohort 1 approximately 50 months after the first patient is randomized in this study. At that time, it is projected that median follow-up time will be 21 months in Cohort 1, and the minimum follow-up time (e.g., for the last patient randomized) is projected to be 7 months. Also on the basis of the assumptions of 120 DFS events required and a target HR of 0.60, it is projected that an observed HR of 0.70 or better in the DFS analysis will result in a statistically significant difference between treatment arms (i.e., HR of 0.70 is the minimally detectable difference for that analysis).

A summary of the assumptions and characteristics of the DFS analysis for Cohort 1 is shown in [Table 1](#).

For Cohort 1, on the basis of the assumptions of a target HR of 0.60, 120 DFS events would provide 80% power to detect a 16% absolute increase in the 2-year DFS rate (50% vs. 66%, corresponding to a 40% risk reduction; i.e., HR of 0.60).

2.3.2 Cohort 2

The final analysis of the primary endpoint of DFS for Cohort 2 will take place when approximately 105 DFS events have occurred, on the basis of the following assumptions:

- Two-sided, stratified log-rank test at the 0.05 significance level
- 80% power
- Median DFS for the control arm of 7.7 months and estimated median DFS in the vemurafenib treatment arm of 13.3 months (which corresponds to an HR of 0.58)
- 5% annual loss to follow-up for DFS
- No interim analysis

Assuming an accrual rate of 5 patients per month in Cohort 2 and a 27-month ramp-up period to reach steady-state enrollment, approximately 175 patients will be required to be enrolled in Cohort 2 over 40 months in order to observe 105 DFS events.

A summary of the assumptions and characteristics of the DFS analysis for Cohort 2 is shown in [Table 1](#).

For Cohort 2, on the basis of the assumptions of a target HR of 0.58, 105 DFS events would provide 80% power to detect a 17% absolute increase in the 2-year DFS rate (12% vs. 29%, corresponding to a 42% risk reduction; i.e., HR of 0.58).

Table 1 Assumptions and Characteristics for Disease-Free Survival Analyses by Cohort

	Cohort 1	Cohort 2
Patients enrolled	300	175
Hazard ratio targeted	0.60	0.58
Target median (control)	24 months	7.7 months
Target median (vemurafenib)	40 months	13.3 months
Final DFS analysis		
Number of DFS events	120	105
MDD hazard ratio ^a	0.70	0.68
α level (two sided)	0.05	0.05
Power	80%	80%

DFS=disease-free survival; FPI=first patient in; MDD=minimum detectable difference.

Note: A 5% annual dropout rate is anticipated for DFS analyses.

^a Minimally detectable difference; the largest observed hazard ratio that is projected to be statistically significant.

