4.4.1 Primary Efficacy Endpoint

The primary endpoint, DFS, is defined as the time from randomization until the date of the first local, regional, or distant melanoma recurrence, occurrence of new primary melanoma, or death from any cause. The DFS component of melanoma recurrence will be assessed by the investigator. The DFS component of an occurrence of a new primary melanoma will be based upon the diagnosis made by a Roche-designated central pathology laboratory. For patients without a DFS event at the time of data cutoff, data will be censored at the date of the last disease assessment. For patients who are treated with any non-protocol anti-cancer therapy (defined as systemic therapy or radiation therapy) without a DFS event, the data will be censored at the date of the last disease assessment. For patients without a DFS event for whom no post-randomization disease assessment is available, the data will be censored on the randomization date.

For patients whose recurrence has been proven histologically, the date of melanoma recurrence will be defined as the earliest date of the scan or clinical examination that prompted the biopsy. For patients whose suspicious lesions were deemed not amenable to biopsy (see Protocol Section 4.5.1.4) or for patients who refuse a biopsy, the date of melanoma recurrence will be defined as the earliest date of the scan or clinical examination that would have prompted a biopsy. For patients with an occurrence of a new primary melanoma, the date of the new primary melanoma will be defined as the earliest date of the clinical examination or scan that prompted the biopsy.

The duration of DFS will be calculated as the earliest DFS event date or censoring date minus the randomization date plus 1 day, converted to months.

The final analysis of the primary endpoint of DFS will take place when approximately 120 DFS events have occurred for Cohort 1 and approximately 105 DFS events have occurred for Cohort 2 (see Section 2.3). The final DFS analyses for both cohorts will be conducted at the same time by using the dataset from the same data cutoff date for both cohorts. The primary efficacy analyses will be comparisons of the two treatment groups, using a two-sided,

stratified log-rank test for Cohort 1 and Cohort 2 separately. The statistical significance of the two DFS tests is defined by the rule outlined below.

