The hierarchical testing procedure, whereby Cohort 2 is tested first, will be used to adjust for comparison of two treatment groups (vemurafenib vs. control) for the two cohorts, in order to maintain an overall Type I error rate of 0.05 (two sided) for the final analysis of the primary endpoint of DFS. If the p-value for Cohort 2 is ≤ 0.05 , i.e., the vemurafenib treatment group is statistically significantly different from the control group in Cohort 2, then, Cohort 1 will be tested. If the p-value for Cohort 1 is ≤ 0.05 , then the vemurafenib treatment group is also statistically significantly different from the control group in Cohort 1. That is:

- Step 1: If $p_2 \leq 0.05$, then vemurafenib treatment group is statistically significantly different from the control group in Cohort 2. Go to step 2.
- Step 2: If $p_1 \leq 0.05$, then vemurafenib treatment group is also statistically significantly different from the control group in Cohort 1.

p_1 and p_2 are the p-values of final DFS analyses in Cohort 1 and Cohort 2, respectively.

Median DFS time will be estimated using the Kaplan–Meier method, and the two-sided 95% CI will be calculated using the method of Brookmeyer and Crowley (1982) for each cohort. In addition, Kaplan-Meier methodology will be used to estimate landmark (e.g., 1-year, 2-year, and 3-year) DFS rates and the associated two-sided 95% CIs for each treatment arm, and the Kaplan-Meier curves will be provided. The HR for DFS (recurrence, new primary melanoma, or death) and the associated two-sided 95% CI will be computed using a stratified Cox proportional hazards model.

The stratification factors in the stratified analyses are the stratification factors used in randomization of patients in each cohort. For Cohort 1, stratified analyses will incorporate two stratification factors: pathologic stage (Stage IIC, Stage IIIA, and Stage IIIB) and region (North America, Australia/New Zealand/South Africa/Latin America, rest of the world). For Cohort 2, stratified analyses will incorporate one stratification factor, region (North America, Australia/New Zealand/South Africa/Latin America, rest of the world).

As a sensitivity analysis, an unstratified log-rank test will be performed and the unstratified HR will be provided for each cohort.

In addition, the following sensitivity analyses will be performed for DFS by study cohort:

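### The 80% power printed for Cohort 1 DFS is stand-alone power; under the SAP 4.4.1 testing order the chance of declaring Cohort 1 significant is about 64% at the printed event targets and about 70% at the projected common cutoff

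*SAP*

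**What the plan says.** SAP 2.3.1 sizes Cohort 1 on a two-sided 0.05 log-rank test with a target HR of 0.60 and concludes that "120 DFS events would provide 80% power to detect a 16% absolute increase in the 2-year DFS rate". Table 1 prints 80% for both cohorts: 120 events at HR 0.60 in Cohort 1, and 105 events at HR 0.58 in Cohort 2. For Cohort 1 the text adds that "it is projected that an observed HR of 0.70 or better in the DFS analysis will result in a statistically significant difference". Footnote a to Table 1 defines the minimally detectable difference (MDD) as "the largest observed hazard ratio that is projected to be statistically significant".

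Two remarks near these figures bear on how to read them. SAP 2.2 says "The sample size determination was evaluated separately for each cohort", and SAP 2.3 says that the DFS "analyses for the two cohorts will be conducted according to the procedure specified in Section 4.4.1".

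SAP 4.4.1 then says "The statistical significance of the two DFS tests is defined by the rule outlined below". The rule begins "The hierarchical testing procedure, whereby Cohort 2 is tested first, will be used to adjust", and it moves on to Cohort 1 only if the Cohort 2 p-value is at most 0.05. The same section adds "The final DFS analyses for both cohorts will be conducted at the same time by using the dataset from the same data cutoff date".

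The Protocol repeats the power and HR 0.70 statements in its synopsis and Section 6.1.1, and the 80% and the footnote in Table 4. Section 6.1 refers to 6.4.1, which leaves the detailed testing procedure to the SAP. The Protocol's statistical sections therefore do not show the order of testing. The rationale for Protocol Version 10 does mention hierarchical testing.

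**The concern.** A power figure in a sample-size section is normally read as the chance that the planned analysis will support a claim if the target effect is true. For Cohort 1 a claim needs two results: significance in Cohort 2 and significance in Cohort 1. The printed 80% covers only the second. Neither document gives the probability of both.

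The HR 0.70 sentence goes further, because it describes the outcome of an observed result. Under SAP 4.4.1 a Cohort 1 HR of 0.70 or below cannot be declared significant if Cohort 2 has failed.

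Cohort 1 holds 300 of the 475 planned patients. At stake is whether a reader of the plan sees the real chance of a formal DFS conclusion in the larger cohort.

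**Working it through.** **Inputs** (SAP 2.3, Table 1 and 4.4.1): Cohort 1, 120 events, HR 0.60, medians 24 and 40 months, 300 patients over 43 months with a 17-month ramp-up. Cohort 2, 105 events, HR 0.58, medians 7.7 and 13.3 months, 175 patients over 40 months with a 27-month ramp-up. Both: 1:1 allocation, two-sided 0.05, 5% annual loss.

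**1. Reproduce the printed figures.** Schoenfeld power is Φ(√(d/4)·|ln HR| − 1.96).
- Cohort 1: √30 × 0.5108 − 1.96 = 0.838; Φ = 0.799.
- Cohort 2: √26.25 × 0.5447 − 1.96 = 0.831; Φ = 0.797.
- Critical HRs: exp(−1.96/√30) = 0.699 and exp(−1.96/√26.25) = 0.682, matching the printed 0.70 and 0.68.

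So the 80% and the MDDs are those of each cohort's own test at full alpha, with no condition on the other cohort.

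**2. Apply the sequence at the printed targets.** The cohorts contain different patients, so the two tests are independent once the true HRs are fixed. The chance of declaring Cohort 1 significant is 0.797 × 0.799 = 0.637. Simulating the two steps gives 0.638.

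**3. Apply it at one cutoff.** The 120/105 pair does not fall on one date under the plan's own projections. Assume exponential DFS, 5% annual loss, both cohorts opening together, and accrual scaled to 300 over 43 months and 175 over 40 months. The ramp shape is not given, so take a linear ramp-up and uniform accrual as two cases.

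| | Linear ramp | Uniform |
|---|---|---|
| Month Cohort 2 reaches 105 events | 42.4 | 38.5 |
| Month Cohort 1 reaches 120 events | 50.8 | 47.5 |
| Cohort 2 events at that later date | 131.5 | 132.8 |
| Cohort 2 power | 0.878 | 0.881 |
| Cohort 1 overall (× 0.799) | 0.701 | 0.704 |

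At a fixed month-50 cutoff both event counts move:
- Linear ramp: 117.1 and 129.6 events, 0.789 × 0.873 = 0.689.
- Uniform: 128.4 and 137.7 events, 0.825 × 0.892 = 0.736.

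**4. Upper limit with 120 Cohort 1 events.** If all 175 Cohort 2 patients had events, Cohort 2 power would be 0.950, and 0.950 × 0.799 = 0.759.

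**5. The HR 0.70 sentence.** At the target effect, P(observed Cohort 1 HR ≤ 0.70) = Φ(√30 × ln(0.70/0.60)) = 0.801. The chance of this together with Cohort 2 failing is 0.801 × (1 − 0.797), about 16%, at 105 Cohort 2 events. At the common cutoff in step 3 it is 0.801 × (1 − 0.88), about 10%.

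**The case against.** The best defence is that no printed power is miscalculated and the basis is partly disclosed. SAP 2.2 says the cohorts were sized separately, the reference to Section 4.4.1 stands just above the Cohort 1 text, and Protocol 3.3.2 presents the cohorts as powered in their own right. Both powers and the rule are in the SAP, so a reader can multiply them. Test-level power is also the plan's general habit. The OS powers in SAP Table 2 (0.45 and 0.49) reproduce as stand-alone values (0.454 at 107 deaths, 0.491 at 118), although OS is tested only after DFS and DMFS. Finally, Protocol Version 10 postdates the primary analysis, so planning power no longer drives a decision.

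Much of this stands. It shows that the 80% is sound as stand-alone power and that the matter is minor. It does not supply the overall figure, and it does not repair the HR 0.70 sentence or the footnote, which say what will be significant while SAP 4.4.1 defines significance otherwise.

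A reader might also infer that SAP Version 4 created the gap by moving Cohort 2 from 120 to 105 events. The figures do not support that. At the target effects the product was 0.799 × 0.799 = 0.638 before (120 events, HR 0.60) and 0.637 after (105 events, HR 0.58). It falls to 0.744 × 0.799 = 0.595 only if Cohort 2's HR is held at 0.60, and the Version 4 rationale itself prints the corresponding 74% for Cohort 2.

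**Conclusion.** Wrong as written, but minor. For Cohort 1 the 80% is stand-alone power, or power conditional on Cohort 2 success. The probability of declaring Cohort 1 significant is about 10 to 16 percentage points lower: about 64% at the printed targets and about 70% when the common cutoff is set by Cohort 1 reaching 120 events. At a fixed month 50 it is about 69% to 74%, depending on accrual shape.

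The 64% uses printed inputs only. The 70% rests on the assumptions in step 3 of the working. In particular, linear ramps at the stated peak rates yield only about 276 and 132 patients, so accrual had to be scaled to the stated totals. It also relies on Cohort 1 being the later cohort to reach its target, as the planning figures imply. If Cohort 2 were the later one, the figure would move back toward 64%.

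A reader might infer that the sample size was miscalculated, that the family-wise error is not controlled, or that the reported result is in doubt. None of these follows. The calculation reproduces, the fixed order controls Type I error, and the conclusion reported in the Protocol is the one the SAP rule requires.

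**What to change.** In SAP 2.3.1 and Table 1, and correspondingly in the Protocol synopsis, Section 6.1.1 and Table 4:

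- Label the Cohort 1 80% as stand-alone power, equal to power conditional on Cohort 2 being significant.
- Add the overall figure: *Under the SAP Section 4.4.1 sequence, overall power for Cohort 1 is about 64% at 120/105 events and HRs 0.60/0.58, and about 70% at a common cutoff when Cohort 1 reaches 120 events (about 131 to 133 Cohort 2 events), assuming exponential DFS, 5% annual loss, both cohorts opening together, and accrual scaled to 300 patients over 43 months and 175 over 40 months.*
- Qualify the HR 0.70 sentence and the MDD footnote: *for Cohort 1, only if Cohort 2 is also significant (SAP Section 4.4.1).*

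The cost is a few lines of text and one less favourable planning figure. Protocol 3.3.2 and the multiplicity procedure can stay as they are.

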3. STUDY CONDUCT

3.1 RANDOMIZATION ISSUES

After written informed consent has been obtained and eligibility has been established, each patient will be assigned an identification number and randomized to one of the two treatment arms with the use of an interactive voice or Web response system (IxRS). As noted in Section 2, randomization will be stratified by pathologic stage (Stage IIC, Stage IIIA, Stage IIIB) and region (North America, Australia/New Zealand/South Africa/Latin America, rest of the world) in Cohort 1 and by region (North America, Australia/New Zealand/South Africa/Latin America, rest of the world) in Cohort 2. A stratified, permuted, block randomization scheme will be used to obtain approximately a 1:1 allocation between the two treatment groups.

3.2 INDEPENDENT REVIEW FACILITY

An independent review facility will not be used for this study.

3.3 DATA MONITORING

An independent Data Safety Monitoring Board (DSMB) will be employed to evaluate safety data from this study as specified in the DSMB Charter.

4. STATISTICAL METHODS

Descriptive summaries of continuous data for each cohort will include the mean, standard deviation, median, minimum, and maximum, and number of patients. Descriptive summaries of discrete data for each cohort will include the number of patients and incidence as a frequency and percentage.

The baseline value of any variable will be defined as the last available value prior to the first administration of study treatment.

4.1 ANALYSIS POPULATIONS

4.1.1 Intent-to-Treat Population

The intent-to-treat (ITT) population is defined as all randomized patients, whether or not study treatment was received. The ITT population will be analyzed according to the treatment assigned at randomization.

4.1.2 Safety Population

The safety population will include all patients who receive at least one dose of study treatment. Patients who receive at least one dose of vemurafenib will be included in the vemurafenib safety population. The safety population will be analyzed according to the patients' safety group.

4.1.3 Pharmacokinetic-Evaluable Population

The PK-evaluable population will include all patients who have received at least one dose of vemurafenib and have provided valid PK assessments. The PK-evaluable population will be analyzed according to the treatment received. The PK population at specific timepoints will vary, depending on the availability of results at confirmed dosing and PK assessment times.

4.2 ANALYSIS OF STUDY CONDUCT

Enrollment, eligibility violations, and patient disposition will be summarized for randomized patients by treatment arm. The summary of patient disposition will include whether treatment was completed or discontinued prematurely and the reason for premature treatment discontinuation. Study treatment administration will be summarized by treatment arm for all treated patients.

4.3 ANALYSIS OF TREATMENT GROUP COMPARABILITY

Demographic variables, stratification factors, and other baseline characteristics will be summarized for the ITT population by cohorts.

4.4 EFFICACY ANALYSIS

Unless otherwise specified, all efficacy analyses will be performed on the ITT population. The primary and all secondary objectives of this study will be evaluated separately for each cohort.

